9.6.2 Body Weight

Baseline body weight will be summarized using the descriptive statistics outlined in Section 9 to characterize the enrolled Safety Population. Changes from baseline will be described using the descriptive statistics for continuous outcomes. In addition, potentially clinically meaningful changes will be evaluated using the descriptive statistics for categorical endpoints described. The definitions of clinically meaningful changes will be provided in the SAP.

9.6.3 Vital Signs

Vital signs include blood pressure, heart rate, respiration rate and body temperature. Vital signs data will be listed and summarized using descriptive statistics for absolute values, and changes from baseline by visit and dose group. In addition, potentially clinically meaningful changes will be evaluated using the descriptive statistics for categorical endpoints. The definitions of clinically meaningful changes will be provided in the SAP.

9.6.4 Electrocardiogram Parameters

ECG parameters of interest include PR interval, QRS duration, QT interval, and QTcF. Baseline values will be summarized by descriptive statistics to characterize the Safety Population. Changes from baseline will be summarized using the descriptive statistics described in Section 9 for continuous outcomes. In addition, potentially clinically meaningful changes will be evaluated using the descriptive statistics for categorical endpoints. The definitions of clinically meaningful changes will be provided in the SAP.

9.6.5 Clinical Laboratory Panels

Clinical laboratory panels include serum chemistry, hematology, and urinalysis, as well as coagulation and serum hormone markers. Baseline values will be summarized by descriptive statistics or frequency tables, where appropriate, to characterize the Safety Analysis Set. Changes from baseline will be summarized using the descriptive statistics described in Section 9 for continuous outcomes. In addition, the count and percentage of participants with at least one clinically significant abnormal value by visit and post treatment will be summarized by dose group. Data listings of abnormalities will also be provided as appropriate.

9.6.6 Columbia Suicide Severity Rating Scale

Baseline and post-baseline results for the C-SSRS will provided in patient listings. The count and percentage of participants with suicidal behavior and suicidal ideation (as assessed by C-SSRS) will be summarized by visit and dose group.

9.7 Other Analysis

Demographics (age, gender, race, ethnicity, and region) and other baseline disease characteristics, including APOE4 genotype, will be summarized using descriptive statistics.

Analyses of biomarkers, pharmacogenomic, and PK data will be described in separate reports outside the context of the SAP.

9.8 Analyses for Long-term Extension

For the LTE, the incidence and severity of AEs over the placebo-controlled and long-term extension periods of the study will be summarized from LTE baseline to the end of treatment by DB Intervention Period treatment assignment and overall. Other safety parameters will be summarized as described for the DB Intervention Period primary analysis in Section 9.6.

Analyses for the LTE will use the same methods as described for the DB Intervention Period analysis in Sections 9.3 through 9.5. Summaries will be provided for changes from LTE baseline by DB treatment assignment and overall. For participants switching from placebo to active treatment, a two-slope random coefficient model will be used to compare the change in biomarkers and efficacy assessments from DB baseline to Week 24 (e.g., end of DB Intervention period) and from the LTE baseline (e.g., Week 24) to Week 60 (end of LTE).

A full description of LTE analyses will be provided in the SAP.

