Intervention Assignment Method / Arms	 Randomized 1:1:1 to once daily ASN51 , ASN51 , or placebo (n = 26/dose level) Randomization stratified by baseline Alzheimer's treatment (symptomatic treatment [with an acetylcholinesterase inhibitor or memantine] versus no), and APOE4 status (carrier or non-carrier) Following the 24-week DB Intervention Period, participants randomized to placebo will receive ASN51 (randomized 1:1 to during the dose-blind LTE Period. Participants initially randomized to ASN51 will continue at the DB-assigned dose level. 						
Population / Sample Size	 Adults (50 to 80 years) with mild cognitive impairment due to Alzheimer's disease or mild Alzheimer's disease dementia, collectively termed early Alzheimer's disease, with plasma pTau217 positivity as evidence of amyloid pathology Approximately 78 participants are planned across three arms (n = 26 per arm). Assuming a 20% dropout rate, approximately 21 participants per arm are expected to complete the study. 						
Key Eligibility Criteria	 Key Inclusion Criteria Male or female age 50 to 80 years A clinical diagnosis of AD at either the mild cognitive impairment or mild AD dementia stage per National Institute on Aging and the Alzheimer's Association, consistent with Stage 3 and Stage 4 in the FDA draft guidance for early AD Mini-Mental State Examination score of 20 to 28 (inclusive) A plasma pTau217 result consistent with the presence of amyloid pathology (defined as > 0.18 pg/mL) Must have a care partner who, in the Investigator's judgment, has frequent and sufficient contact with the participant (at least 10 hours/week) as to be able to provide accurate information about the participant's cognitive and functional abilities. The care partner must be literate and provide informed consent. Key Exclusion Criteria Any medical or neurological/neurodegenerative condition (other than AD) that, in the opinion of the Investigator, might be a contributing cause to the participant's cognitive impairment (e.g., current history of substance abuse, uncontrolled vitamin B12 deficiency or abnormal thyroid function, stroke or other cerebrovascular condition, normal pressure hydrocephalus, Parkinson's disease, Lewy body dementia, cerebral amyloid angiopathy, frontotemporal dementia) or could lead to discontinuation, lack of compliance, interference with study assessments, or safety concerns 						

[figure not shown]
	Non-amnestic presentation of AD as judged by the Investigator

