2.2.2 Risk Summary

2.2.2.1 Intervention Risks and Mitigation

2.2.3 Overall Benefit: Risk Conclusion

3 OBJECTIVES AND ENDPOINTS

Objectives	Endpoints							
Primary								
To evaluate the safety and tolerability of daily doses of ASN51 as compared with placebo	Incidence and severity of AEs Changes from baseline in laboratory safety assessments (including clinical chemistry, hematology, urinalysis, and serum hormone markers), Changes from baseline in vital signs, 12-lead electrocardiograms, and physical (including neurological) examinations Changes from baseline in C-SSRS							
Key Secondary								
To evaluate the effect of daily doses of ASN51 as compared with placebo on the pathophysiology of early AD To evaluate the effect of ASN51 versus placebo in change from Baseline to Week 24 on the pathophysiology of early AD	Change from baseline through Week 24 in CSF pTau217 Change from baseline through Week 24 in CSF total tau protein Change from baseline through Week 24 in plasma pTau217							
Other Secondary								
To evaluate the effect of daily doses of ASN51 as compared with placebo on tau pathology in early AD	Change from baseline through Week 24 in MK-6240 tau PET signal							
To evaluate the pharmacokinetics of ASN51 in early AD	Trough (C _{min}) at steady state and maximum (C _{max}) concentration of ASN51 in plasma at steady state through Week 24							
Tertiary/Exploratory								
To evaluate the effect of daily doses of ASN51 as compared with placebo on the pathophysiology of early AD To evaluate the effect of ASN51 versus placebo in change from Baseline to Week 24 on biomarkers of early AD	 Change from baseline through Week 24 in biomarkers, including but not limited to: Plasma Phosphorylated tau 181, GFAP, Aβ42/40, NFL CSF Phosphorylated tau 181, microtubule binding region tau 243, GFAP, Aβ42/40, NFL, neurogranin 							

ct of daily doses of with placebo on in early AD Change from baseline through Week 24 in: CDR-SB score ADAS-Cog13 score MMSE score ADCOMS score						
com Baseline to cructure Change from baseline through Week 24 in volumetric brain MRI parameters (e.g., whole brain volume, lateral ventricular volume, and cortical thickness measures of certain brain regions)						
Extension Period						
-term safety and 1 in early AD The incidence and severity of AEs over the DB placebo-controlled and LTE periods of the study						

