4 TRIAL DESIGN

4.1 Description

ASN51-201 is a multi-site, placebo-controlled, double-blind, randomized, parallel group trial with a long-term extension (LTE). The purpose of the trial is to evaluate the safety, PK, effect on biomarkers of disease pathophysiology and pathology, and preliminary effects on measures of clinical efficacy of multiple doses of ASN51 in adults with early AD.

The trial design is depicted in Section 1.2.

Screening for eligibility will be conducted using a tiered approach and may be completed over multiple days. An abbreviated screening informed consent process may be utilized to conduct initial prescreening (i.e., denoted Tier 1 and Tier 2 per Table 1), if allowed at the investigative site. Participants who meet Tier 1 eligibility criteria, including MMSE, should proceed to Tier 2 (plasma pTau217). Tier 1 and Tier 2 assessments may take place on the same day.

Informed consent for the full trial must be obtained prior to performing any Tier 3 and Tier 4 screening procedures 2 per Table 1. Participants may proceed to Tier 4 only after all criteria from Tier 1, 2, and 3 have been met.

The duration of the Screening Period may be up to 8 weeks (may be extended on a case-by-case basis by the Sponsor Medial Monitor) to allow for the completion of assessments and for the evaluation of required laboratory, ECG, and imaging tests per the Schedule of Activities provided in Table 1.

Dose selection has been enabled by two Phase 1 target engagement trials that utilized an OGA enzyme PET ligand to define the precise relationship in human beings between plasma concentration and brain target occupancy. Further details on dose selection can be found in Section 6.2.

Eligible participants will be randomized in a 1:1:1 ratio to one of the following planned arms:

- ASN51: once daily by mouth
- ASN51: once daily by mouth
- Placebo once daily by mouth.

Eligible participants will self-administer ASN51 once daily at the assigned dose level during a 24-week Double-blind (DB) Intervention Period. The participant (accompanied by a designated study partner) will be asked to return to the investigative site approximately every 4 weeks over two days as long as all assessments are completed within the visit window.

[figure not shown]
Following completion of the DB Intervention Period, all participants will be offered continued ASN51 in the 36-week LTE Period. Participants initially randomized to placebo will receive ASN51 (randomized 1:1

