ASN51 will continue at the assigned dose level, unless dose modification is recommended based on emerging data.

A safety Follow-up Visit will take place 4 weeks after the last dose of ASN51.

A Schedule of Activities for the DB Intervention Period and LTE Period are provided in Table 2 and Table 3, respectively.

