6.6.3 Randomization

Participants will be randomized (1:1:1) to ASN51 at 1 of 2 dose levels, or placebo.

The randomization schedule will be computer generated by the Sponsor or designee. An IWRS will be used.

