8.4.1 Time Period and Frequency for Collecting Adverse Event Information

All AEs, SAEs, AESI, and partner pregnancies occurring during the protocol-specified timeframes (Table 7) will be assessed and reported per guidelines provided in Section 12.

Table 7 Adverse Event Reporting Periods

Event Type	Reporting Period	Additional Requirements
AE/SAE during Screening Period	Date of participant informed consent through start of Day 1 Visit (prior to first dose of IMP)	Report as AE/SAE only if related to trial-specified procedure (medical history otherwise)
Treatment-emergent AE/SAE	First dose of IMP through 4 weeks post final dose of IMP	Report SAEs outside of reporting period if assessed as related to IMP
AESI	First dose of IMP through 4 weeks post final dose of IMP	Report AESI outside of reporting period if assessed as related to IMP
Pregnancy of partner	Date of participant informed consent through 4 weeks post final dose of IMP	Obtain consent to follow partner pregnancy

AE = adverse event; AESI = adverse event of special interest; IMP = investigational medicinal product; SAE = serious adverse event.

Clinically significant changes from baseline in any safety or clinical laboratory parameter will be recorded as AEs or SAEs, if deemed appropriate by the Investigator.

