9.1.2 Safety Analysis Set

The Safety Analysis Set consists of all participants who receive at least one dose of IMP. This analysis set will be used for the analyses of all safety endpoints. Participants will be included based on the actual dose level received.

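### Section 9.8 counts LTE adverse events from LTE baseline although the endpoint spans both periods, and its grouping by double-blind arm puts two ASN51 doses in the placebo-origin row

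*Combined protocol and SAP*

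**What the plan says.** Section 3 lists the LTE safety endpoint as "The incidence and severity of AEs over the DB placebo-controlled and LTE periods of the study". Section 9.8 begins with the same two periods, but its operative words are that the events "will be summarized from LTE baseline to the end of treatment by DB Intervention Period treatment assignment and overall".

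Section 9.1.2 gives the general rule for safety data: "This analysis set will be used for the analyses of all safety endpoints. Participants will be included based on the actual dose level received".

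The LTE allocation is in the Synopsis (1.1), where "participants randomized to placebo will receive ASN51 (randomized 1:1 to during the dose-blind LTE Period", and again in Section 4.1. The dose values are blacked out in both places. Section 6.6.3 gives the number of dose levels: "Participants will be randomized (1:1:1) to ASN51 at 1 of 2 dose levels, or placebo". Under Section 4.1, the original ASN51 arms stay on their assigned dose "unless dose modification is recommended based on emerging data".

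Table 7 (Section 8.4.1) sets the treatment-emergent reporting period as "First dose of IMP through 4 weeks post final dose of IMP". Section 9.8 sends the other LTE safety parameters to Section 9.6 and leaves the full LTE description to the SAP.

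**The concern.** There are two separate problems.

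- **Window.** A table that starts at LTE baseline is not a table of events over both periods. Someone programming from Section 9.8 cannot satisfy both halves of its sentence. The half that states the counting rule is the one that misses the Section 3 endpoint.
- **Grouping.** Double-blind assignment is no longer the treatment being taken by people who started on placebo. In the LTE they are all on ASN51, apparently at two doses. A row labelled by their original arm hides the dose at which their first ASN51 exposure took place. Section 9.10 describes a dose-ranging trial sized on safety objectives, so an AE row that cannot be read by dose works against its purpose.

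**Working it through.** **The plan's own figures.** Completers per arm: 26 × 0.80 = 20.8, or about 21, as the Synopsis states. Section 9.10, rule of 3: 3/21 = 14.3%, matching its figure of about 14%. The exact value is 1 − 0.05^(1/21) = 13.3%. None of these is disputed.

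**Window.** The Synopsis gives 24 double-blind weeks and 36 LTE weeks. For the original ASN51 arms, the share of planned ASN51 time before LTE baseline is 24/(24 + 36) = 24/60 = 40%. For switchers, LTE baseline is their first ASN51 exposure, so the start does not cut any ASN51 time. It leaves out only their 24 placebo weeks, which the Section 3 endpoint includes.

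**Is a cumulative AE table specified elsewhere?** Section 9 assigns Sections 9.1 through 9.7 to the Week 24 primary analysis. Section 9.8 carries Sections 9.3 through 9.5 into the LTE, and Section 9.6 for safety parameters other than AEs. LTE adverse events therefore rest on the contradictory sentence alone.

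**Grouping.** The number entering the LTE is not stated. I assume 21 placebo-origin entrants (the planned completers), with 26 (all randomized to the arm) as the upper end.

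| Placebo-origin entrants | Per dose at 1:1 |
|---|---|
| 21 | 10 and 11 |
| 26 | 13 and 13 |

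An invented illustration: an event in 3 of 10 at one dose (30%) and 0 of 11 at the other (0%) would appear as 3/21 = 14%, which describes neither dose.

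**What splitting the row can show.** With zero events in n people, the one-sided 95% upper bound is 1 − 0.05^(1/n):

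- n = 10: 25.9%
- n = 11: 23.8%
- n = 13: 20.6%

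The split row is therefore weak on its own. Counting everyone ever exposed to a dose over both periods gives 21 + 10 = 31 up to 26 + 13 = 39 people, and the bound falls to 9.2% and 7.4%. Those people have unequal follow-up (up to 60 or 36 planned weeks on ASN51), so exposure time has to stand beside the counts.

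**The case against.** The strongest reply is that the LTE is exploratory, that Section 9.8 defers its full description to the SAP, and that the pieces of a sound table are already there. The Synopsis says the primary and final analyses use similar methods. Section 9.2 gives its AE overview within each dose group. Section 9 plans a combined ASN51 summary, so some pooling is deliberate. This supports a low severity but does not remove the conflict. Deferral covers missing detail, whereas here a stated rule disagrees with the endpoint, and an SAP that expands Section 9.8 would inherit it. A combined ASN51 column does not show events by dose. If Section 9.1.2 were confined to the Week 24 analysis, the conflict with it would go, but nothing would then call for LTE events by dose.

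A reader might infer more than the documents support:

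- **That double-blind arm is the only grouping.** Section 9.8 also has an overall summary. It pools further, so it does not help, but it is there.
- **That early events are lost.** They are collected, and the primary analysis reports them.
- **That every LTE safety table is affected.** Section 9.6.3, for example, summarizes vital signs by dose group.
- **That the original ASN51 arms are misgrouped.** For them the two rules differ only if a dose is modified or misallocated.
- **That events in the last 4 weeks are dropped.** Section 9.8 does not define where treatment ends for this purpose or say that later events are excluded. Citing Table 7 in the SAP would settle it.
- **That events worsening after the switch go unrecorded.** Sections 12.1.2 and 12.2.3 treat worsening as an AE to be documented. Only its attribution in the analysis is open, which is ordinary SAP detail.

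**Conclusion.** The point holds and is minor. Section 9.8 is inconsistent with itself and with Section 3 on the counting window: 40% of planned ASN51 time in the original ASN51 arms lies outside the LTE table. It is also inconsistent with Section 9.1.2 on grouping. The placebo-origin row has nobody on placebo and, very probably, two doses in it: 10 and 11 people if 21 enter, up to 13 and 13 if 26 enter.

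This rests on two assumptions. The first is that re-randomization is to the two dose levels of the trial, which is inferred from the 1:1 split, the dose-blind LTE and Section 6.6.3. The second is the number of entrants, which the documents do not give. The window finding depends on neither. No decision rule uses the table.

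**What to change.** Reconcile Section 9.8 with Sections 3 and 9.1.2, in the protocol text or when the SAP is written:

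1. Add an AE summary from Day 1 through the Table 7 reporting period (4 weeks after the last dose). Assign each event to the treatment actually being taken (placebo, or each ASN51 dose) and show exposure time. This covers both periods, including the switchers' placebo weeks. Counting only from the first ASN51 dose would leave those weeks out and so would not report the Section 3 endpoint.
2. Keep the LTE-only table by double-blind arm and overall, but split the placebo-origin row by LTE dose.

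The rule for events that began on placebo and worsened in the LTE can be left to the SAP. Efficacy and biomarker summaries by original arm need no change.

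The cost is SAP wording and a few table columns, with no new data. The drawback is small counts in the split row: zero events in 10 to 13 people still allows a true incidence of up to 26% to 21%.

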6.6.2 Blinding and Unblinding

The initial 24 weeks of intervention will be administered in a double-blind fashion. Participants, Investigators, site personnel, and the Sponsor and/or designees will be blinded to randomization assignment.

The statistician(s) responsible for generating the randomization schedule, and personnel responsible for preparing trial intervention supplies will be unblinded.

Randomization numbers will be assigned sequentially. Each participant will be dispensed blinded trial intervention (ASN51 or placebo), labeled with the participant's unique randomization number. Unblinding mechanisms will be available by IWRS.

Should any trial stopping criteria (Section 7.4) be triggered the involved participant(s) will be unblinded to randomization assignment by the SRC to determine if the event was related to IMP.

In the event of an emergency, the Investigator has the sole responsibility for determining if unblinding of a participant's randomization assignment is warranted. The safety of the participant will be the first consideration in making such a determination. If a participant's randomization assignment is unblinded, the Sponsor Medical Monitor must be notified within 24 hours.

Following completion of the 24-week DB Intervention Period, data will be unblinded after database lock for the purpose of data analysis; however, participants, Investigators, and study site staff will remain blinded to DB treatment assignment until the end of the 36-week LTE Period (end of the study).

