9 STATISTICAL CONSIDERATIONS

A general description of the statistical methods planned to analyze the safety and preliminary efficacy of the IMP is outlined below. The analyses specified in this protocol will be expanded in the Statistical Analysis Plan (SAP) to include a detailed description of the analyses. The SAP will be finalized and approved prior to database lock.

Trial data will be reported using summary tables, figures, and data listings. Descriptive statistics will be used to summarize the data. For continuous variables, the mean, standard deviation, median, minimum, and maximum will be provided. For discrete data, incidence and percentages will be provided. Statistical tests will be 1-sided at the alpha level of 0.10, unless stated otherwise. P-values will be used descriptively and will have no inferential value. All p-values will be reported to the 3rd decimal place. Summary tables will include the data from the ASN51 groups combined, i.e., Placebo and ASN51 for the DB and LTE periods, respectively.

Baseline for all clinical laboratory evaluations, vital signs measurements, and 12-lead ECGs will be defined as the last evaluation before IMP administration. The timing of each protocol-specified assessment is provided in the Schedules of Activities (Section 1.3).

Two sets of analyses will be conducted. The first set of analyses will be conducted after all participants have had the opportunity to complete the Week 24 assessment or have discontinued the study (primary analysis Sections 9.1 through 9.7). The second set of analyses will be conducted when all participants have had the opportunity to complete the LTE or discontinued the study (Section 9.8).

For endpoints collected only once post-baseline, changes from baseline will be analyzed using an analysis of covariance (ANCOVA) model that includes the categorical effects of APOE4 status, use of AD medication, treatment group, and the continuous covariate of the baseline value of the variable being analyzed. The one-sided p-value (t-test on least squares means at Week 24) and two-sided 80%, and 90% confidence limits will be tabulated. The model will also include the randomization stratification factors (i.e., APOE4 status and use of AD medication).

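### Section 9.8 compares slopes before and after Week 24 in placebo switchers alone, so any time effect shared by all arms is confounded with starting ASN51 in this exploratory analysis

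*Combined protocol and SAP*

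**What the plan says.** Section 9.8 of the protocol states: "For participants switching from placebo to active treatment, a two-slope random coefficient model will be used to compare the change in biomarkers" and efficacy assessments over two periods, double-blind baseline to Week 24 and Week 24 to Week 60. The named model is restricted to the switchers.

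In Section 4.1, "all participants will be offered continued ASN51 in the 36-week LTE Period", and "Participants initially randomized to placebo will receive ASN51 (randomized 1:1" between the doses, so no one stays on placebo after Week 24. Under Section 6.6.2, participants and sites "will remain blinded to DB treatment assignment until the end of the 36-week LTE Period". The synopsis calls the extension dose-blind, so participants know they are on active drug but not which arm they came from.

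Section 9.8 also reuses the methods of Sections 9.3 to 9.5 for the extension, summarises changes from extension baseline by double-blind arm and overall, and leaves the full description to the SAP. It links none of this to the two-slope comparison. The synopsis makes the extension objectives exploratory, and Section 9 makes p-values descriptive.

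**The concern.** The question is whether starting ASN51 changes the course of the disease measures. A one-group comparison of slopes asks something narrower: is the mean slope the same before and after Week 24? The two questions coincide only if, without drug, the measure runs in a straight line for 60 weeks and nothing but the drug changes at Week 24.

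Two features of this trial could break that condition:

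- **Practice.** ADAS-Cog13 is absent from the screening schedule (Table 1). It is first given at Day 1 and repeated at Weeks 12 and 24 (Table 2). An early retest gain falls in the placebo segment, makes it look too good, and makes the ASN51 segment look worse by comparison.
- **Expectancy.** From Week 24 everyone knows they take ASN51. A lift from that knowledge falls in the second segment and looks like benefit.

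In a model fitted to switchers alone, neither can be separated from the drug. At stake is the interpretation of the one analysis in Section 9.8 aimed at the effect of starting ASN51 in the placebo arm: it could suggest harm or benefit where there is none, or hide a real effect.

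**Working it through.** **The plan's own figures.** The plan gives no power or error rate for the two-slope comparison. Its one power figure (Section 9.10: 90%, 21 per arm, difference 20%, SD 25%, one-sided alpha 0.10) reproduces. The noncentrality is (20/25) × √(21/2) = 2.59 on 40 df, which gives 0.900. The same n and alpha are used below.

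**Inputs from the documents.** Cognitive visits at Weeks 0, 12, 24, 36, 48 and 60 (Tables 2 and 3); 21 completers per arm (Section 9.10), hence 21 switchers and 42 ASN51 continuers; one-sided alpha 0.10 (Section 9); higher ADAS-Cog13 is worse (Section 8.2.1.2).

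**Assumptions.** Everyone enters and completes the extension. Slope SD is 0.08 points/week in each period, with correlation 0.7 between the two slopes. Residual SD σ is 2.5 to 4 points. Practice is a gain of 1 or 2 points by Week 12 that persists. Expectancy is a gain of 2 points at every visit after Week 24. The documents give none of these sizes.

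**Step 1: the estimator.** With complete balanced data, the model's slope change equals the mean over participants of D = Σ w·y, from a piecewise-linear fit with a knot at Week 24. The weights are w = (0.0439, −0.0044, −0.0526, −0.0241, 0.0044, 0.0329). Any straight line gives D = 0, so under exact linearity the test rejects at its nominal 10%.

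**Step 2: bias with no drug effect.**

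- A practice gain g lowers every visit after the first. The weights sum to zero, so the bias is +0.0439 × g per week: 0.0439 for 1 point, 0.0877 for 2.
- A 2-point expectancy gain gives −2 × (−0.0241 + 0.0044 + 0.0329) = −0.026 per week.

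**Step 3: precision.** Var(D) = 2 × 0.08² × (1 − 0.7) + σ² × Σw² = 0.00384 + 0.006396 × σ².

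- σ = 2.5: variance 0.0438, SD 0.209, SE = 0.209/√21 = 0.0457
- σ = 4: variance 0.1062, SD 0.326, SE = 0.326/√21 = 0.0711

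**Step 4: rejection rates of the planned test, no drug effect** (noncentral t, 20 df, noncentrality = bias/SE).

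| Scenario | Wrong conclusion | σ = 4 | σ = 2.5 |
|---|---|---|---|
| Exactly linear | either | 10% | 10% |
| Practice 1 point | worsening | 25% | 37% |
| Practice 2 points | worsening | 47% | 73% |
| Expectancy 2 points | benefit | 18% | 24% |

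A half-point practice gain gives about 16% to 21% false worsening.

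**Step 5: contrast with continuers.** Subtract the slope change in the 42 participants randomized to ASN51. Time effects shared by the arms cancel, so under no drug effect the contrast has mean zero and rejects at 10%. Simulated rates over linear, shift, practice and accelerating courses were 0.095 to 0.106. The price is a standard error √(1 + 21/42) = 1.22 times larger.

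**Step 6: behaviour under a real effect.** Take −0.10 points/week and σ = 3, so SD(D) = √(0.00384 + 0.006396 × 9) = 0.248. The SE is 0.0541 for the planned test and 0.0662 for the contrast. The background is linear.

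| Onset delay after first dose | Mean D, switchers | Mean D, continuers | Power, planned | Power, contrast | Contrast shows harm |
|---|---|---|---|---|---|
| None | −0.100 | 0 | 70% | 59% | <1% |
| 12 weeks | −0.084 | −0.053 | about 60% | 21% | 4% |
| 24 weeks | −0.039 | −0.100 | 29% | 1% | 35% |

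With immediate onset plus a 2-point practice gain, the planned test falls to about 14% (mean −0.100 + 0.088 = −0.012), while the contrast stays at 59%.

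**The case against.** **Status.** The extension is exploratory, p-values are descriptive, and Section 9.8 names no null, alpha level or decision for this model. That stands. A reader might infer that a false efficacy or safety conclusion would follow for the trial. The documents do not support that: no primary or key secondary result depends on this comparison.

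**Other summaries.** Continuers will be reported at the same visits in the by-arm summaries. That gives context, but it puts no control for time inside the two-slope comparison.

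**Practice.** A reader might extend the practice argument equally to all three cognitive scales. Table 1 shows the MMSE given at prescreening and the CDR-SB at screening, and Section 8.2.1.3 describes the CDR as a semi-structured interview of participant and partner. Only ADAS-Cog13 is new at Day 1, and the practice figures are for that scale alone.

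**Expectancy.** Section 8.2.1 keeps raters blinded throughout, and double-blind participants already had a two-in-three chance of active drug. Both limit the likely size.

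**Assay batches.** "The first set of analyses will be conducted after all participants have had the opportunity to complete the Week 24 assessment", so extension samples could be assayed or read in later batches. A reader might infer a batch shift at Week 24, but the available text describes no batching. It is a possibility, not a finding, and is not counted here.

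**CSF.** Week 60 CSF is optional (Table 3), so 21 versus 42 does not describe it.

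**The remedy.** The contrast carries its own strong assumption, a constant ASN51 slope effect from Day 1. The delayed-onset rows above show how badly it can fail. This objection stands in full, and it is why the contrast should accompany the switchers-only estimate.

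**Conclusion.** The concern holds as an interpretation problem in an exploratory analysis. The switchers-only slope change cannot separate starting ASN51 from any non-linear course or any change at Week 24 that all arms share. That follows from the design, whatever the size of the nuisance effects.

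The size rests on assumptions. For ADAS-Cog13 practice gains of 1 to 2 points, false worsening occurs in about 25% to 73% of trials against 10%. For a 2-point expectancy gain, false benefit occurs in 18% to 24%. If the untreated course is linear, the planned test keeps its nominal level and is the more powerful of the two.

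A reader might conclude that the comparison with continuers is simply the correct test and should take over. It is valid under no drug effect, but with delayed onset it is the less reliable of the two. Neither estimate is adequate alone; read together, they show which assumption the conclusion depends on.

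**What to change.** In Section 9.8, and in the SAP before the extension analysis is finalised:

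1. Fit the two-slope model to all three double-blind arms, with arm-by-period slope terms.
2. Report the slope change at Week 24 in placebo switchers minus that in participants randomized to ASN51, pooled and then by dose, beside the switchers-only estimate.
3. State that the switchers-only change rests on linear untreated progression and is not by itself evidence of a drug effect.
4. State that the contrast assumes a constant ASN51 slope effect from Day 1, and define what it estimates when that fails.
5. Say that rates per week are compared, since the two periods last 24 and 36 weeks.

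The cost is a few sentences and no new data, visits or procedures. The contrast is less precise (standard error about 1.22 times larger; power 59% instead of 70% in the example with linear progression and immediate onset). With late onset it can lose most of its power or point the wrong way, so it should not be reported alone.
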